1.3 Correlative Studies

All correlative studies will be collected under HRPO# 201011766 (“Tissue Acquisition for Analysis of Genetic Progression Factors in Hematologic Diseases”) that all patients will be concurrently enrolled in. The goals of the correlative studies include:

1. To correlate patient-specific mutations with response to decitabine.
We will perform exome sequencing of each patient’s pre-study bone marrow sample and skin sample. We will determine AML/MDS-associated variants found in the bone marrow, but not skin sample. We will correlate the presence of mutations with response (especially mutations in *DNMT3A*, *IDH1*, *IDH2*, and *TET2*). This study is powered to identify mutations with >80% sensitivity to predict decitabine response if used as a clinical assay.
2. To correlate the velocity and depth of response with response to decitabine.
We will assess tumor burden by allele frequency of patient-specific mutations in bone marrow samples collected pre study, Cycle 1 Day 10±1, Cycle 1 Day 28±4, and Cycle 2 Day 28±4. We will assess mutations in at least 24 recurrently mutated genes (including, but not limited to: *FLT3*, *DNMT3A*, *NPM1*, *TET2*, *WT1*, *IDH1*, *IDH2*, *RUNX1*, *NRAS*, *TP53*, *U2AF1*, *KRAS*, *PHF6*, *MSTP9*, *PTPN11*, *KIT*, *SMC3*, *PRUNE2*, *ETV6*, *CEBPA*, *SMC1A*, *ASXL1*, *STAG2*, *RAD21*) as well as all patient-specific mutations discovered during exome sequencing. The leukemic allele frequency will be measured using the Illumina MySeq or HiSeq platform using DNA capture by gene specific biotinylated-oligonucleotides. Patient bone marrow samples will be assessed pre-study, Cycle 1 Day 10 ± 1, Cycle 1 Day 28 ± 4, and Cycle 2 Day 28 ± 4 and compared with patient specific skin samples (normal control). The velocity of response will be calculated as the natural log rate of patient-specific mutation allele frequency clearance. Depth of response will be defined as the lowest patient-specific mutation

allele frequency in a bone marrow sample. The velocity and depth of tumor response will be correlated to:

- Achievement of clinical CR,
- Time to best response,
- Mutational status,
- Time to disease progression.

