5.2.8 Cycles 1, 2, 4 and 6 Day 28 ± 4 days

Bone marrow aspirate and biopsy. Standard bone marrow procurement procedures will be followed for collection of the tissue. Assessments performed on bone marrow will include: correlative studies (collected under HRPO# 201011766), morphologic assessment, cytogenetics, and FISH.

Patients who achieve with clinical response (CRi or better) and are receiving cycles every 6 weeks, will undergo bone marrow biopsies on day 42 ± 4.

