A power analysis was performed using Chi-square test for the association between mutation and response to decitabine. The frequency of *DNMT3A*, *IDH1/2*, and *TET2* mutations in AML and MDS patients are each between 15% and 30% in multiple cohorts.[29-37] **Table 3** shows the minimal detectable differences of response rates between mutant and wild-type cases, assuming an expected overall 45% CR/CRi rate and 80% power. For an average of 20% frequency of a mutated gene, for example, 100 patients will provide 80% power to detect 30% difference at a 2-sided 0.1 alpha error. The purpose of this study is to determine whether any of these mutations result in a clinically significant association that would warrant pre-treatment testing. We believe that a reasonable cut off would be if at least 30% of clinical response could be attributed to the presence of a specific mutation. However, we anticipate that more power could be achieved as we assess patient groups with combined characteristics (e.g. *DNMT3A* mutation or loss of *DNMT3A* expression). In addition, we expect that the majority of the enrolled 125

Table 3. Detectable mutation associated response rates (80% power, $\alpha = 0.05$)

Total N	% of patients with a given mutation	Detectable response difference	Sensitivity of mutation to predict response at minimum detectable response difference*
100	15%	0.40	80%
	20%	0.35	75%
	30%	0.30	67%
	40%	0.27	61%
	50%	0.26	58%

* Assuming the overall response rate (CR/CRi) of 45%

patients can be used in the analysis (since all of our molecular information will be acquired within 30 days of enrollment, we anticipate a drop-out rate of 20% or less).

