14.2.3 Secondary Endpoint Analyses

The overall response rate (CR/CRi/PR) and complete response rate (CR/CRi) will be compared with historical controls[2], and the 95% confidence intervals will be provided.

The rate of patient specific mutation clearance after 10, 28, and 56 days of therapy will be determined using an Illumina based platform. We will compare the rate of mutation clearance between the patients who achieve a CR/CRi after 4 cycles and those who do not. We anticipate that we will identify between 6 and 25 exonic SNVs per case (the range obtained with >200 AML samples sequenced to date with whole genome or exome sequencing), and that the expected 95% confidence interval of the mean variant allele frequency will be $\pm 2.56\%$ and $\pm 1.25\%$,

respectively, if we assume an anticipated standard deviation of 3.2% within the same clone. The change of tumor burden over time and its association with clinical response will be assessed using 2-way ANOVA for repeated measurement data, followed by the ad-hoc multiple comparisons for between-group differences (e.g., responders vs. non-responders) at given time points as well as the between-time differences within each group. The resultant critical P values will also be corrected using permutation analysis for multiple testing.

The percent decrease in bone marrow methylcytosine will be calculated on day 10 ± 1 . We will compare this reduction with previously published data and between the patients who achieve CR/CRi and those who do not. The correlation of peak plasma levels of decitabine with response will be assessed using 2-sample t-test or Mann-Whitney non-parametric rank-sum test as appropriate. The change of total bone marrow DNA methylcytosine from baseline and its association with both steady-state plasma drug levels and response will be assessed using 2-way ANOVA for repeated measurement data, followed by the ad-hoc multiple comparisons for between-group differences (e.g., responders vs. non-responders) and between-time differences. Similar analyses will be performed for the correlation of expression profiles and SNP analysis with pharmacokinetic data.

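### The tumor-burden comparison uses repeated-measures ANOVA with no rule for a missing Cycle 2 marrow; in its classical form this loses early non-responders, and a mixed model on all marrows would serve better

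*Combined protocol and SAP*

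**What the plan says.** Section 14.2.3 commits the tumor-burden analysis to one method: "The change of tumor burden over time and its association with clinical response will be assessed using 2-way ANOVA for repeated measurement data". Pairwise contrasts come next; in the plan's words, the ANOVA is "followed by the ad-hoc multiple comparisons for between-group differences (e.g., responders vs. non-responders) at given time points". The same section sets the times, "The rate of patient specific mutation clearance after 10, 28, and 56 days of therapy will be determined", and compares clearance rates "between the patients who achieve a CR/CRi after 4 cycles and those who do not". Section 1.3 names the material: "bone marrow samples collected pre study, Cycle 1 Day 10±1, Cycle 1 Day 28±4, and Cycle 2 Day 28±4".

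Sections 14.1 to 14.3 contain no rule for a patient who lacks one of these marrows: no complete-case statement, no imputation, no mixed model and no sensitivity analysis. The only allowance is in Section 14.2.2, "we anticipate a drop-out rate of 20% or less", and its stated reason is that all molecular data are in hand within 30 days of enrollment. The efficacy-evaluable set in Section 14.1 requires only one cycle of treatment.

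On timing, Section 5.2.8 says that patients in CRi or better who "are receiving cycles every 6 weeks, will undergo bone marrow biopsies on day 42" (± 4 days, counted within the cycle). The ANOVA wording is the same in all five protocol versions in the file.

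**The concern.** Classical two-way repeated-measures ANOVA needs a value in every patient-by-time cell. As usually run, it removes a patient with one missing marrow entirely, including the samples already sequenced. It also treats everyone's Cycle 2 sample as taken at the same time.

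The missing samples would not be a random subset. Section 5.3 lets treatment end at any time for progression, death, adverse event, withdrawal and other reasons. A patient who leaves before the Cycle 2 marrow without CR/CRi falls in the non-responder group. If such patients tend to have high or rising VAF, the non-responders who remain look better than the full group, and the contrast with responders shrinks. Velocity and depth of mutation clearance form a listed secondary objective (Section 2.2), so the contrast matters to the trial's aims.

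**Working it through.** **1. The plan's own figures.** Section 14.2.3 gives tumor-clearance power per clone. I used a two-sample t-test with n variants at each of two time points, noncentrality d / (SD × √(2/n)), 2n − 2 degrees of freedom and alpha 0.05. Sidedness is not stated; two-sided is assumed.

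| Variants, difference | SD 3.2%: plan / recomputed | SD 4.7%: plan / recomputed |
|---|---|---|
| 6, 10% | >99% / 99.8% | 91% / 91.2% |
| 3, 15% | >98% / 98.6% | 82% / 82.8% |

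The confidence half-widths also reproduce: 1.96 × 3.2/√6 = 2.56 and 1.96 × 3.2/√25 = 1.25. The figures are sound for what they describe. Their unit is the variant within a clone, so they do not address how many patients have a Cycle 2 marrow.

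**2. The drop-out allowance.** 125 × (1 − 0.20) = 100, which matches the plan's N. The reason given covers 30 days. The Cycle 2 Day 28 marrow falls at 28 + 28 = 56 days, so the reason does not cover it.

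**3. Who could be lost.** Assume 125 enrolled and 45% response: 56.25 responders and 68.75 non-responders. As a worst case, take every missing Cycle 2 marrow to be in a non-responder.

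| Missing, % of enrolled | Non-responders lost | Non-responders left | Responder share of completers |
|---|---|---|---|
| 5% | 6.25/68.75 = 9% | 62.5 | 47% |
| 10% | 12.5/68.75 = 18% | 56.25 | 50% |
| 20% | 25/68.75 = 36% | 43.75 | 56% |

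**4. Effect on the day-56 contrast when early failures follow their own course.** Assumed mean VAF (%) from day 0 to day 56: responders 40 to 5, later failures 40 to 28, early failures 40 to 48. Take 45 responders and 55 non-responders, with 10 or 20 of the 55 failing before day 56.

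- Complete cases: 28 − 5 = 23 points.
- Everyone, 10 early failures: (45 × 28 + 10 × 48)/55 − 5 = 26.6. Shrinkage (26.6 − 23)/26.6 = 14%.
- Everyone, 20 early failures: (35 × 28 + 20 × 48)/55 − 5 = 30.3. Shrinkage (30.3 − 23)/30.3 = 24%.

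**5. Effect when drop-out depends only on the observed day-28 VAF.** In a separate simulation (45 versus 55 patients, true day-56 difference −21 points, 23% drop-out overall, 32% of non-responders), complete cases gave −19.4. Shrinkage is (21 − 19.4)/21 = 8%. That drop-out is above the plan's 20% ceiling. At 14% drop-out the non-responder mean moved only from 33.1 to 32.4.

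**6. What a mixed model recovers.** Under step 5, which is missing at random by construction, it gave −20.7 against −21. Under step 4 it did much less. Across two sets of 40 simulated trials, a random intercept gave 23.4 to 23.7 (10 early failures) and 24.0 (20). A random slope gave 23.8 to 23.9 and 24.2 to 25.3. Set against 26.6 and 30.3, that is at most about a third of the gap.

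**7. Timing.** A switch to 6-week cycles after Cycle 1 puts the Cycle 2 marrow at 28 + 42 = day 70, which the ANOVA would enter as day 56.

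**The case against.** The strongest reply is that the protocol never says patients without a Cycle 2 marrow are dropped. That is correct. Deletion is the usual behavior of the named method, and an analyst could fit the same layout as a mixed model. A reader might infer that the plan discards these patients; the text supports only that it names a method whose classical form does so and sets no rule to prevent it.

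Second, many failures will have the sample. Response is judged after four cycles, and the schema printed in other versions of the file removes progressors after two cycles, about when this marrow is due. Only exits before it matter. It is also unclear whether an exit sample exists: Section 5.2.9 lists no correlative work on the end-of-study marrow, while footnote d of Appendix 2 calls for it at every time point. Even if collected, a marrow on an unscheduled day has no cell in the ANOVA.

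Third, the day-10 and day-28 contrasts and the clearance rate can use early failures if run on available data. This stands, and it limits the loss.

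Fourth, the day-70 problem does not affect all responders. It needs CRi or marrow CR after Cycle 1 and a discretionary switch then; a switch after Cycle 2 leaves the day-56 sample alone.

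Fifth, a reader might extend the point to methylcytosine, whose "association with both steady-state plasma drug levels and response will be assessed using 2-way ANOVA for repeated measurement data". The documents do not support that. It is measured only pre-study and at Cycle 1 Day 10, so no day-56 marrow is involved and, with two time points, sphericity holds trivially.

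**Conclusion.** The point holds as a worthwhile, low-cost improvement to a secondary analysis. The stated method has no rule for a foreseeable and informative kind of missing data, and the 30-day rationale does not reach the Cycle 2 marrow.

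The direction, toward a smaller contrast, rests on early failures having higher VAF than other non-responders. That is plausible but not documented. The 8% to 24% range rests wholly on assumed curves and drop-out patterns, and its upper end uses the worst case in which all missing marrows are in non-responders. Nothing here shows that a conclusion of the trial would change. A reader might infer that the mutation–response result is compromised; it is not, because the primary analysis in Section 14.2.2 uses pre-study mutation status and does not depend on the Cycle 2 marrow.

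**What to change.** For tumor burden only, in Section 14.2.3:

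- Replace the ANOVA with a linear mixed model fitted by REML, with response group, time and their interaction, using every available marrow and actual study day, with a random slope or unstructured covariance.
- Analyze VAF on its own scale, or on the log scale with a floor stated in advance, since the log is undefined once a mutation clears to zero.
- State how death or discontinuation before the Cycle 2 marrow is handled, and report missing marrows by response group and visit.
- Add a sensitivity analysis restricted to day 0–28 clearance, because the mixed model recovers only part of the bias if early failures follow a different course.

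In Section 14.2.2, correct the statement that all molecular information is acquired within 30 days. Leave the methylcytosine analysis as it is on this point.

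The cost is SAP wording and slightly more analysis work in standard software, with no new samples. The downside is reliance on a missing-at-random assumption, which the sensitivity analysis is there to probe.

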8.0 CORRELATIVE STUDIES SAMPLE COLLECTIONS

Bone marrow samples will be collected pre-study, on Cycle 1 Day 10 ± 1 , and on Day 28 ± 4 of Cycle 1, 2, 4, and 6 for correlative studies. Following Cycle 6, bone marrow biopsies should be performed at the discretion of the treating physician to assess for relapse or progression. The bone marrow samples will be collected under HRPO# 201011766 (“Tissue Acquisition for Analysis of Genetic Progression Factors in Hematologic Diseases”) that all patients will be concurrently enrolled in.

Skin biopsy sample will be collected as part of the patient’s participation in HRPO# 201011766 (“Tissue Acquisition for Analysis of Genetic Progression Factors in Hematologic Malignancies”). There is no required time frame for this sample, and it may have been collected months or even years prior to the first dose of decitabine.

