Statistical power justification. A power analysis was performed using two-sample t-test for between-group difference and paired t-test for the change over time. For tumor clearance, this will provide $> 99\%$ power to detect a 10% difference in the means at two separate time points for clones with 6 or more variants, and $> 98\%$ power to detect a 15% difference if there are 3 or more variants per clone with $\alpha = 0.05$ (power will decrease to 91% and 82%, respectively, in cases where the standard deviation is 4.7%, the maximum we have observed thus far). For pharmacologic correlations, we anticipate 85% power to determine a 25 ng/ml difference between the average C_{\max} of 45 evaluable responders and 55 evaluable non-responders with an anticipated average C_{\max} of 70 ng/ml and a standard deviation of 40 ng/ml within the entire cohort, and with $\alpha = 0.05$. [22] We believe a less significant difference would not be sufficient to warrant application in clinical decision making (i.e. whether to continue therapy for more than 1 cycle). We anticipate 99% power to determine a difference of 20% in the reduction of bone marrow methylcytosine between 45 evaluable responders and 55 evaluable non-responders with an expected standard deviation of 15% and $\alpha = 0.05$. [28, 66-68] The difference in methylcytosine reduction previously observed was 30% between patients achieving CR/PR and those with only hematologic improvement. [28]

Time to relapse and time to death will also be listed for each patient.

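### The clearance power (over 99%) is for variants within one clone, not for the planned patient comparison, and the 85% Cmax power relies on a plasma sample that the leading protocol text does not schedule

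*Combined protocol and SAP*

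**What the plan says.** **Clearance.** Section 2.2 makes the velocity and depth of mutation clearance a secondary biomarker. Section 14.2.3 sets the comparison: "We will compare the rate of mutation clearance between the patients who achieve a CR/CRi after 4 cycles and those who do not". It adds a repeated-measures ANOVA of responders against non-responders. The power paragraph in the same section claims more than 99% power "to detect a 10% difference in the means at two separate time points for clones with 6 or more variants", and more than 98% "power to detect a 15% difference if there are 3 or more variants per clone with" alpha 0.05. These fall to 91% and 82% at an SD of 4.7%. The base SD comes from the text just before: "respectively, if we assume an anticipated standard deviation of 3.2% within the same clone". The paragraph names a two-sample t-test for group differences and a paired t-test for change over time.

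**Plasma.** Section 14.2.3 states: "The correlation of peak plasma levels of decitabine with response will be assessed". It also relates steady-state levels to methylcytosine. Its power paragraph says: "For pharmacologic correlations, we anticipate 85% power to determine a 25 ng/ml difference", for 45 responders against 55 non-responders with an SD of 40 ng/ml. Section 1.1 lists plasma levels among the correlates of response. In the protocol text that opens the file, however, Section 8.0 covers marrow ("Bone marrow samples will be collected pre-study, on Cycle 1 Day 10" and later visits) and a skin biopsy only. Sections 1.3, 2.2 and 5.2 schedule no plasma sample, and the flow chart in Appendix 2 keeps a Cycle 1 Day 4 column with nothing in it.

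**Timing.** Section 14.2.3 assesses clearance at 10, 28 and 56 days. Under Section 5.2.8, responders on six-week cycles "will undergo bone marrow biopsies on day 42" ± 4.

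**The concern.** A power figure is useful only for the comparison it was computed for. The clearance comparison is between patients, so its precision depends on how many patients there are and how much they differ from one another. The stated figure would be the same with two patients or two hundred. The other between-group claims in the same paragraph (Cmax and methylcytosine) do use 45 against 55 patients, so clearance is the exception. If the over-99% figure were carried into a report, a null clearance result could be taken as close to definitive when the plan contains nothing to justify that.

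The Cmax claim has a different fault. The arithmetic is sound, but the measurement it needs is not in the schedule, so the analysis cannot be delivered as powered for patients treated under that text.

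**Working it through.** **1. Reproduce the clearance figures.** Inputs, all from Section 14.2.3: differences of 10 and 15 points, 6 and 3 variants, SD 3.2 and 4.7, alpha 0.05. Sidedness is not stated there; two-sided reproduces the figures. For a two-sample t-test with n variants at each of two time points, the noncentrality is (d/SD)·√(n/2) on 2n − 2 degrees of freedom. For a paired test it is (d/SD_diff)·√n on n − 1 degrees of freedom.

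| Variants, difference, SD | Stated | Two-sample | Paired, SD_diff = SD | Paired, SD_diff = SD·√2 |
|---|---|---|---|---|
| 6, 10, 3.2 | >99% | 99.8% | >99.9% | 98.8% |
| 3, 15, 3.2 | >98% | 98.6% | 96.2% | 81.0% |
| 6, 10, 4.7 | 91% | 91.2% | 98.3% | 83.5% |
| 3, 15, 4.7 | 82% | 82.8% | 78.6% | 54.9% |

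For example, in the first row (10/3.2)·√3 = 5.41 on 10 degrees of freedom.

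The two-sample column matches all four figures. No single paired correlation can. At SD 4.7, the 82% for 3 variants needs SD_diff below SD, because SD_diff = SD already gives only 78.6%. The 91% for 6 variants needs SD_diff above SD, because SD_diff = SD gives 98.3%. So the paired test named for change over time is not the source, and n is the number of variants in a clone. The stated confidence-interval half-widths have the same basis: 1.96 × 3.2/√6 = 2.56 and 1.96 × 3.2/√25 = 1.25.

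**2. Make the patient the unit.** With 45 against 55, √(1/45 + 1/55) = 0.201. The detectable difference at 80% power is (1.96 + 0.8416) × 0.201 = 0.563 SD by the normal approximation and 0.57 SD by exact t. The between-patient SD is not in the documents, so the following is a range by assumption (exact t, two-sided 0.05):

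| Assumed between-patient SD (points) | Power for 10 points |
|---|---|
| 10 | 99.8% |
| 15 | 91% |
| 20 | 69% |
| 25 | 50% |
| 30 | 38% |

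For 10 points, 99% power needs an SD of about 11.5 or less, and 80% needs 17.6 or less. For 15 points, 98% power needs 18.4 or less.

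**3. Cmax.** With 25/40 = 0.625 SD, the noncentrality is 0.625/0.201 = 3.11 on 98 degrees of freedom. Power is 86.8%, within 2 points of the stated 85%. If only N patients have plasma, split about 45:55, power is 14% at N = 10, 32% at 25, 58% at 50, 76% at 75 and 87% at 100. The documents do not give N.

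**4. Where plasma appears.** The file holds five versions of the protocol. The first four schedule no plasma sample. The last collects 3 mL on Cycle 1 Day 4 (its Sections 1.3, 2.2, 5.2.5 and 8.0 and its study calendar). Its Section 1.3 treats that sample as an exception to the tissue-banking protocol, so that protocol does not supply it by default.

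**5. Timing.** If Cycle 2 is a six-week cycle, its marrow falls nominally on day 28 + 42 = 70 instead of 28 + 28 = 56. With both windows at ± 4 days, the gap within the cycle can be anything from 38 − 32 = 6 to 46 − 24 = 22 days.

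**The case against.** The arithmetic is right, and the clearance figure is labelled for what it is: change between two time points in a clone. Section 14.2.3 also plans comparisons over time within each group. The sample size rests on Table 3 and the staged accrual in Section 14.3, not on this figure, and the endpoint is a secondary biomarker in a single-arm phase II study. All of that stands. It limits the consequence but does not give the between-patient comparison a power statement.

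Several stronger readings are tempting, and the documents do not support them:

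- **The clearance comparison is underpowered.** This cannot be shown. A between-patient SD near 10 would give more than 99% power.
- **The sponsor regards detection of a responder difference as nearly certain.** The text never attaches the 99% to that comparison.
- **There can be no plasma data.** Version dates are on removed pages, and patients enrolled under the last version in the file may have stored samples. Outright deletion could discard them.
- **Later marrow sampling in responders biases velocity.** Section 1.3 defines velocity as a log rate of clearance, and sampling later does not shift a rate per day. Only depth and visit-based comparisons are exposed, and only for patients who respond after Cycle 1 and whose physician lengthens the cycle. A fixed gap of at least 14 days ignores the windows, and Section 6.1 allows infection holds that can delay anyone.
- **The ANOVA would mostly lose non-responders.** The documents give no drop-out by response.

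**Conclusion.** Both main points hold, and the power statements are wrong as written for the design they sit in. The clearance figures are within-patient precision. The patient-level power is unstated and, without a between-patient SD, unknown: 99.8% to 38% for 10 points over assumed SDs of 10 to 30. The 85% Cmax figure cannot stand for patients treated under text that schedules no plasma. For any patients with stored plasma it must be recomputed on their number. Calling the Cmax text a leftover assumes that the version opening the file is the current one. The agreement of four of the five versions makes that likely, but no date confirms it. The timing point is minor. The methylcytosine power in the same paragraph is already at patient level (45 against 55, 20 points, SD 15, over 99.9%) and is not affected.

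**What to change.** 1. In Section 14.2.3, keep the variant-level figures only as within-patient assay precision, and name the test that produced them. Add the patient-level statement: 45 against 55 gives 80% power for a difference of 0.57 between-patient SD. Say which patient-level summary that SD describes (log rate per day, or allele frequency at a visit), and give an SD with its source or the range above. The first 25 patients, whose clearance rates Section 14.3 expects to have calculated, could supply one.
2. Remove the peak and steady-state plasma analyses and the 85% power from Section 14.2.3, and plasma levels from Section 1.1. Alternatively, restrict them to patients with plasma stored under the version that collected it, state that number, and recompute the power.
3. Analyse allele frequency by actual days since first dose rather than nominal day 56. A mixed model of log allele frequency is one reasonable way to do this, not a required one.

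The cost is wording and a little modelling, with no extra patients or procedures. The stated clearance power becomes conditional on an SD and may look less favourable.
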